4.1.1 Inclusion Criteria

Patients must satisfy all the following criteria to be included in the study:

1. Male and female patients aged 21 to 80 years (both inclusive)
2. Patients who have tested positive for SARS-CoV-2 by RT-PCR assay using a respiratory tract sample (either nasopharyngeal swab OR oropharyngeal swab OR nasal aspirate OR tracheobronchial aspirate) collected within 72 hours prior to randomization
3. Patients should be hospitalized
4. Patients having moderate or severe COVID-19* with a score of > 4 on the 10-point ordinal scale of clinical status used by WHO in the SOLIDARITY trial, at baseline assessment [i.e., patients with blood oxygen saturation (SpO₂) <95% at rest on room air at sea level and requiring supplemental oxygen].

*Note: This includes patients clinically assigned as:

- I. 'moderate' COVID-19
 - a. symptoms which could include fever, cough, sore throat, malaise, headache, muscle pain, gastrointestinal symptoms or shortness of breath with exertion and/or clinical signs, such as respiratory rate ≥ 20 breaths per minute or heart rate ≥ 90 beats per minute
 - AND
 - b. blood oxygen saturation (SpO₂) of 94% at rest on room air at sea level
- II. 'severe' COVID-19
 - a. symptoms which could include any symptom of moderate illness or shortness of breath at rest, or respiratory distress and/or clinical signs, such as respiratory rate ≥ 30 per minute or heart rate ≥ 125 per minute
 - AND
 - b. blood oxygen saturation (SpO₂) $\leq 93\%$ on room air at sea level or PaO₂/FiO₂ <300*

Study code: NV-05-983-2020
 Protocol No.: CVD-04-CD-001
 Sponsor name: [name], Limited
 Clinical Study Protocol

The above-mentioned definitions of COVID-19 severity are adapted from the FDA Guidance document COVID-19: Developing Drugs and Biological Products for Treatment or Prevention - Guidance for Industry Final Document dated May 2020²⁴

5. Female patients of childbearing potential*

- a. must have a negative serum pregnancy test at screening
- b. should not be lactating; and not planning to become pregnant/breast feed during the treatment period and for 7 days after the last dose of study medication.
- c. should commit to the use of **TWO** forms of study-acceptable contraception methods, including a barrier method (eg. diaphragm) along with one or more of the following methods of contraception for the duration of the treatment period and for 7 days after the last dose of study medication:

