9. Changes over time in patient's clinical status on the 8-point ordinal scale
- a. Time (no. of days) from randomization to attain clinical status score of 4 or lower
 - b. Proportion of patients in whom clinical status score of 4 or lower has been attained by Days 4, 7, 10, 14, 21 and 28 or discharge (if discharge happens earlier than one or more of the above-mentioned time points)
 - c. Time (no. of days) from randomization to attain clinical status score of 3 or lower
 - d. Proportion of patients in whom clinical status score of 3 or lower has been attained by Days 4, 7, 10, 14, 21 and 28 or discharge (if discharge happens earlier than one or more of the above-mentioned time points)
 - e. Time (no. of days) from randomization to clinical status score improvement by 1 and by 2 points (from baseline)
 - f. Proportion of patients for whom clinical status score improvement by 1 and by 2 points has been attained by Days 4, 7, 10, 14, 21 and 28 or discharge (if discharge happens earlier than one or more of the above-mentioned time points)
10. Changes over time in findings on chest X-ray
11. Changes over time in the National Early Warning Score-2 (NEWS)
12. Percentage of patients requiring, until Day 28 or discharge from hospital (if discharge happens earlier)
- a. Management in intensive care unit
 - b. High Flow Nasal Oxygen or Non-invasive mechanical ventilation
 - c. Invasive mechanical ventilation
13. Time (no. of days) from randomization to:
- a. Management in intensive care unit

Statistical Analysis Plan
Sponsor: [name], Inc

Study Number: NV-05-983-2020

Version: 2.0 Date: 06JAN2021

- b. High Flow Nasal Oxygen or Non-invasive mechanical ventilation
- c. Invasive mechanical ventilation

over an assessment period from randomization until Day 28 or discharge from hospital (if discharge happens earlier)

14. Duration (no. of days) the patient requires:

- a. Management in intensive care unit
- b. Oxygen supplementation
- c. High Flow Nasal Oxygen
- d. Non-invasive mechanical ventilation
- e. Invasive mechanical ventilation

over an assessment period from randomization until Day 28 or discharge from hospital (if discharge happens earlier)

15. Percentage of patients:

- a. dying from any cause
- b. dying from a COVID-19 associated complication

Over an assessment period from randomization until Day 28 or discharge from hospital (if discharge happens earlier).

Stage II

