9.6 Sample Size Calculation

Based on review of published literature, a hazard ratio of 1.25 is reported (adjusted for the stratification in randomization) for time to clinical improvement in COVID-19 patients receiving anti-viral intervention. The hazard ratio of 1.25 is also assumed to be constant throughout the study as per the assumptions of the Cox proportional hazards regression model with the expected average probability of the event over the course of the study to be 0.9 and 0.8 in test and control group respectively. Inequality testing of the hazard ratio using the Cox proportional hazards regression model with 371 subjects in Favipiravir group and 371 subjects in Placebo group achieves 80% power at the 0.05 significance level for an actual hazard ratio of 1.25 assuming the hazard ratio is 1 under the null hypothesis and that the total number of events achieved is 631. Based on the above assumption and considering the dropout rate to be 5%, overall, 390 patients will be randomized in each treatment group. i.e. 780 patients in total to be randomized in the study. The sample size is estimated using nQuery version 8.5.0.0 using Cox proportional hazard regression. Sample size will be re-estimated based on the analysis of results for the primary endpoint observed during interim analyses.

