Time to Management in intensive care unit = Start date of first admission to ICU of the COVID management hospital facility – Date of randomization +1

Time to High Flow Nasal Oxygen supplementation or Non-invasive Mechanical Ventilation = Start date of first administration of high flow nasal oxygen or non-invasive mechanical ventilation (earlier of the two, in case both have been administered) – Date of randomization +1

Time to Invasive mechanical ventilation = Start date of first time Invasive mechanical ventilation – Date of randomization +1

Time (no. of days) for Management in intensive care unit (ICU), High Flow Nasal Oxygen supplementation or non-invasive mechanical ventilation and Invasive mechanical ventilation will be analyzed descriptively. Log-rank test will be used to compare the median time for patients to start “Management in intensive care unit (ICU)”, “High Flow Nasal Oxygen supplementation”, “Non-invasive mechanical ventilation” and “Invasive mechanical ventilation” between the two treatment groups.

14. Duration (no. of days) the patient requires:
- a) Management in intensive care unit
 - b) Oxygen supplementation
 - c) High Flow Nasal Oxygen
 - d) Non-invasive mechanical ventilation
 - e) Invasive mechanical ventilation

Over an assessment period from randomization until Day 28 or discharge from hospital (if discharge happens earlier)

Statistical Analysis Plan
Sponsor: [name], Inc

Study Number: NV-05-983-2020

Version: 2.0 Date: 06JAN2021

Definition of time to Managed in intensive care unit, On Oxygen supplementation, On High Flow Nasal Oxygen Supplementation, On Non-invasive Mechanical Ventilation and On Invasive mechanical ventilation will be as follows:

Number of days Managed in intensive care unit = Stop date of ICU management – start date of ICU management + 1

Number of days On Oxygen supplementation= Stop date of Oxygen supplementation – start date of Oxygen supplementation + 1

Number of days On High Flow Nasal Oxygen = Stop date of High Flow Nasal Oxygen – start date of High Flow Nasal Oxygen + 1

Number of days On Non-Invasive mechanical ventilation= Stop date of Non-Invasive mechanical ventilation – Start date of Non-Invasive mechanical ventilation + 1

Number of days On Invasive mechanical ventilation= Stop date of Invasive mechanical ventilation – Start date of Invasive mechanical ventilation + 1

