Duration (no. of days) for Managed in intensive care unit (ICU), on Oxygen supplementation On High Flow Nasal Oxygen Supplementation, On Non-invasive Mechanical Ventilation and on Invasive mechanical ventilation will be summarized descriptively. ANOVA will be used to compare the mean time(days): “Managed in intensive care unit (ICU), On Oxygen supplementation, On High Flow Nasal Oxygen Supplementation, On Non-invasive Mechanical Ventilation and On Invasive mechanical ventilation” between the two treatment groups.

Note: patients with multiple episodes of Managed in intensive care unit (ICU), On Oxygen supplementation, On High Flow Nasal Oxygen Supplementation, On Non-invasive Mechanical will be summed together and total duration (number of days) will be used for analysis.

15. Percentage of patients
 - a. dying from any cause
 - b. dying from a COVID-19 associated complication

Over an assessment period from randomization until Day 28 or discharge from hospital (if discharge happens earlier).

Patients dying due to any cause and COVID-19 associated complication will be summarized by number and percentage. Two-sided Chi-square test/ Fisher-Exact test at 5% level of significance will be performed to test the difference of proportion between two treatments with two-sided 95% level of significance.

Statistical Analysis Plan
Sponsor: [name], Inc

Study Number: NV-05-983-2020

Version: 2.0 Date: 06JAN2021

Stage II

1. Percentage of patients reporting a clinical relapse of COVID-19 when assessed from day of discharge to 59 days after randomization (Day 60).

Note: 'Clinical relapse' is defined as either the reappearance or worsening of severity (over the assessment on the day of discharge) of one or more of the above-mentioned COVID-19 associated symptoms, or the appearance of any of these symptoms (due to COVID 19 infection) for the first time after discharge.

Percentage of patients reporting a clinical relapse of COVID-19 when assessed from day of discharge to 59 days after the start of study treatment (Day 60) will be summarized by number and percentage. Two-sided Chi-square test/ Fisher-Exact test at 5% level of significance will be performed to test the difference of proportion between two treatments with two-sided 95% level of significance.

2. Proportion of patients
 - a. with disease worsening and requires:
 - v. Admission to ICU
 - vi. High flow nasal oxygen
 - vii. Non-invasive mechanical ventilation
 - viii. Invasive mechanical ventilation

(AND)

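### SAP endpoint 14 durations do not apply the endpoint's own window and are undefined for ITT patients without an episode, so the ANOVA taken literally compares only users of ICU care, high-flow oxygen or ventilation

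*SAP*

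**What the plan says.** SAP 8.2 and 10.6.2 define endpoint 14 as days of ICU care, oxygen, high-flow nasal oxygen, non-invasive ventilation and invasive ventilation, "over an assessment period from randomization until Day 28 or discharge from hospital (if discharge happens earlier"). Section 10.6.2 then gives one formula per component, all of the same form. The oxygen line reads "Number of days On Oxygen supplementation= Stop date of Oxygen supplementation – start date of Oxygen supplementation + 1". None of the five cuts the start at randomization or the stop at Day 28 or discharge. The endpoint 13 formulas, just above, do subtract the date of randomization.

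A note says that a patient's multiple episodes are summed into a total. Nothing is said about a patient with no episode. The analysis is "ANOVA will be used to compare the mean time(days") between the two groups. Section 10.6.2 opens by placing all secondary analyses on the ITT population. Efficacy imputation (SAP 9.5.1) covers only the daily WHO clinical status score.

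Protocol 4.1.1, criterion 4, admits patients with low saturation "at rest on room air at sea level and requiring supplemental oxygen", so every patient has an oxygen need at baseline.

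**The concern.** A patient who never enters ICU, or never has high-flow oxygen, non-invasive ventilation or invasive ventilation, has neither a start nor a stop date for that component. The formula then returns nothing, and a standard ANOVA drops missing outcomes. What remains is a comparison of patients chosen by an event that treatment may influence, which randomization no longer protects. A drug that keeps patients out of ICU altogether gets no credit for them, and if the stays it prevents are the short ones, its remaining users look worse than control.

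Endpoint 14 is the only planned test of days of support. SAP Appendix I also compares ICU, non-invasive and invasive ventilation durations at the unblinded interim, in a paragraph that bases its exploratory analyses on observed data only. A misleading duration comparison could therefore be shown to the DMC, although no formal stopping rule uses it.

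The missing window is a separate fault. Dates outside randomization to Day 28 or discharge can enter the total. For oxygen, the likely intrusion is treatment started before randomization. Because each episode adds 1, support stopped and restarted on the same date would also count that date twice.

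**Working it through.** **The plan's figures.** The documents give no SD, event rate, power or sample size for endpoint 14. They do give the trial size, which supplies the arm size used below. SAP 9.6 states that the design "achieves 80% power at the 0.05 significance level for an actual hazard ratio of 1.25", with event probabilities of 0.9 and 0.8.

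- Events: 4 × (1.960 + 0.842)² / (ln 1.25)² = 630.5, so 631, as stated.
- Patients: 630.5 / 0.85 = 741.8, so 371 per arm, as stated.
- Dropout: 371 × 1.05 = 389.6, so 390 per arm, as stated.

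This sizing reproduces but has no bearing on endpoint 14.

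**Condition for a reversed sign.** Let the control arm have n users with T support days in total, and N patients per arm. Suppose treatment prevents m courses of average length d and leaves the others unchanged.

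- Users-only mean under treatment: (T − md)/(n − m). This exceeds the control mean T/n exactly when d < T/n, that is, when the prevented courses are shorter than average.
- Mean over all N patients, with 0 for non-users: it falls by md/N whatever d is.

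**Illustration (all inputs assumed except N = 390).** ITT in this SAP requires at least one dose, so the true denominator may be slightly smaller. Control has 80 ICU users: 40 stay 4 days and 40 stay 14 days. T = 160 + 560 = 720; users-only mean 720/80 = 9.00; all-patient mean 720/390 = 1.85.

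| Assumed effect | Treated days / users | Users only: treated (difference) | All patients: treated (difference) |
|---|---|---|---|
| Half of short stays prevented | 640 / 60 | 10.67 (+1.67) | 1.64 (−0.21) |
| Half of short and half of long prevented | 360 / 40 | 9.00 (0) | 0.92 (−0.92) |
| Half of long stays prevented | 440 / 60 | 7.33 (−1.67) | 1.13 (−0.72) |

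Row 1 reverses the sign, row 2 hides a halving of ICU days, and row 3 has the right sign.

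Row 1 was also varied over 40 to 120 control users, 25% to 50% of short stays prevented, and stays of 4/14 or 5/20 days. The users-only difference ran from +0.71 to +2.50 days and the all-patient difference from −0.05 to −0.38 days.

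Row 1 was then simulated 2,000 times with user counts fixed and stay lengths drawn as 1 + Poisson, with means 4 and 14. The users-only difference had the wrong sign in 99.95% of runs, and the ANOVA was significant in the wrong direction in about 30%.

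**Oxygen.** If oxygen starts k days before randomization, the literal formula adds k days. The documents do not give k; 0 to 10 days is an assumed range, taken from the symptom-onset limit in exclusion criterion 2. Randomization gives k the same expected value in both arms, so the expected difference does not move. The variance does. With an assumed on-study SD of 6 days and an independent k with SD 2 to 3 days, it rises by a factor of (36 + 4)/36 = 1.11 to (36 + 9)/36 = 1.25.

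**The case against.** The SAP never says that non-users are excluded. It assigns secondary analyses to ITT and sums a patient's episodes, and a sum over no episodes can be read as 0. The window is stated in the endpoint itself, just above the formulas. The assessment schedule first records oxygen, ICU and ventilation details after the first dose on Day 1, and the eCRF is not among the documents, so whether oxygen start dates before randomization are held cannot be checked. Endpoint 12 reports how many patients needed each support (other than standard oxygen) and endpoint 13 compares time to first use, so a drop in users would be visible beside the duration means.

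Much of this stands, and it limits the point. A reader might infer that the SAP prescribes a users-only analysis; it does not, and users-only is what follows if the formula is applied as written. A reader might carry the subset argument over to oxygen; it does not apply there, because every patient requires oxygen at baseline. A reader might take earlier oxygen days as bias; they inflate means and noise but balance in expectation. Same-day restarts matter only if they occur, and nothing in the documents shows how often.

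What does not stand is that the text settles the matter. An ITT label does not create a value where the formula has none, and the formulas conflict with the window above them. Endpoint 12 has a tabulation without a test, and endpoint 13 does not measure days.

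**Conclusion.** The formulas for endpoint 14 are inconsistent with the endpoint's own window and give no value for ITT patients without an episode. Taken literally, the ANOVA for ICU care, high-flow oxygen, non-invasive ventilation and invasive ventilation is a comparison within a post-randomization subset, contrary to the ITT rule. It can miss a real benefit (9.00 against 9.00 days while days per patient fall from 1.85 to 0.92). It can also reverse one (+1.67 against −0.21 days).

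These sizes rest on assumed user counts and stay lengths. The tempting stronger claim, that the analysis will show harm where there is benefit, is not supported: reversal needs the prevented courses to be shorter than average, and the documents say nothing about that. For oxygen the effect is limited to possible inflation of means and variance. Endpoint 14 is one of fifteen secondary endpoints with no stated multiplicity role, and the primary conclusion is unaffected. The change should be made, but the trial's main result does not depend on it.

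**What to change.** Replace the five formulas in SAP 10.6.2 with one rule: the duration is the number of calendar days, from randomization to Day 28 or discharge if earlier, on which the support was recorded, each day counted once. Assign 0 to ITT patients with no such day, and analyse all ITT patients. Use the same derivation for the durations in Appendix I.

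Also state two things that the SAP leaves open:

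- **Deaths.** Under a plain day count, a patient who dies early in ICU scores few days, which looks favourable. Either rank deaths worst, as the SAP already does in its third sensitivity analysis of the primary endpoint, or use support-free days to Day 28 with deaths set to 0.
- **Support ongoing at Day 28.** Count to Day 28 and mark it as truncated.

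With mostly zero values, say whether ANOVA is kept or replaced, for example by a rank test with a bootstrap interval for the mean difference.

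The cost is SAP wording and a new derivation program before the Stage I database lock. Protocol 6.1.3, 6.3.1.3 and 7.1.1.2 already provide for daily collection of ICU, oxygen and ventilation details, so no new data are needed.

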10.6 Efficacy Analysis

10.6.1 Primary Efficacy endpoint

Primary Efficacy endpoint will be as follows:

1. Time to resolution of hypoxia

The primary efficacy endpoint is “Time to resolution of hypoxia (Time frame: Up to 28 days)”

This endpoint will be considered to have been met when the patient has attained a score of 4 or lower on the 10-point ordinal scale of clinical status and either of a) or b), (as applicable) and c) is met:

- a) Score is ≤ 4 on consecutive assessments over the next 5 days, if patient continues to remain in hospital (i.e., has not been discharged).

OR

Statistical Analysis Plan
Sponsor: [name], Inc

Study Number: NV-05-983-2020

Version: 2.0 Date: 06JAN2021

- b) Patient was discharged before five consecutive assessments (after reaching a score of 4)

AND

- c) The patient has survived and has not been re-admitted to hospital for COVID-19 management through Day 28.

*Note: Part c) is applicable to patients in both a) and b).
 i.e. Time to resolution of Hypoxia = either "a and c" OR "b and c" is met.*

Time to resolution of hypoxia will be compared between the treatment groups using the Cox proportional hazard model with age, gender, and baseline score on the 10-point ordinal scale of clinical status as covariates. The hazard ratio and its corresponding two-sided 95% confidence interval (CI) and two-sided p -value at 5% level of significance will be obtained from the above Cox proportional hazard model.

As the patients were in the hospital until discharge, missing data in the daily WHO clinical status score were few. To facilitate the definition of the durable response, a very limited and conservative imputation will be implemented to impute a missing clinical status score if adjacent to a valid score on both sides, the imputed score will be the higher (worse) of the two, as discussed in Section 9.5.1.

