 - 2) The next lowest ranks will be given to patients who do not meet the definition of success but are lost to follow-up or are missing endpoint data for Day 28, but survive to Day 28, beginning with the earliest day for which data are lost for the rest of the study.
 - 3) The next lowest ranks will be given to patients who are informative withdrawals – i.e., they withdraw for a reason related to probable treatment failure – but survive to Day 28, beginning with the withdrawals closest to Day 28 (i.e., the latest withdrawals).
 - 4) The next lowest ranks will be given to patients who are followed to Day 28 but do not meet the primary endpoint definition, beginning with patients with the lowest clinical status score on Day 28.
 - 5) The highest (worst) ranks will be given to patients who die, beginning with the deaths closest to Day 28. Thus, the highest rank will be assigned to the first death.

This sensitivity analysis will be done using ITT population.

Listing will be provided for the 10-point ordinal scale of clinical status and oxygen saturation level.

10.6.2 Secondary Analysis:

All secondary analysis will be done using ITT population.

1. Time to discharge from hospital

Time to discharge from hospital = Date of discharge – Date of randomization +1

Statistical Analysis Plan
Sponsor: [name], Inc

Study Number: NV-05-983-2020

Version: 2.0 Date: 06JAN2021

Time to discharge in days will be summarized descriptively. Time to discharge will be compared between the treatment groups using the Cox proportional hazard model. The hazard ratio and its corresponding two-sided 95% confidence interval (CI) and two sided *p*-value at 5% level of significance will be obtained from the above Cox proportional hazard model; Also Median time, quartile, inter quartile range estimate will be presented.

Patients whose does not discharged up to Day 28 will be right censored as of day 28. Patients who discontinue the study for any reason – withdrawal because of an adverse event or worsening of symptoms, switch to rescue therapy, loss to follow-up, etc. – will be right censored at Day 28.

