 - b. dying

until day 60 (regardless of whether patients are discharged from hospital before Day 28 or not)

Proportion of patients with disease worsening will be summarized by number and percentage. Two-sided Chi-square test/ Fisher-Exact test at 5% level of significance will be performed to test the difference of proportion between two treatments with two-sided 95% level of significance.

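### The tested mortality endpoint stops at discharge, so the final analysis has no tested stand-alone comparison of all-cause Day 28 mortality

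*SAP*

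**What the plan says.** SAP 10.6.2, endpoint 15, reports the percentages of patients dying from any cause and from a COVID-19 complication "Over an assessment period from randomization until Day 28 or discharge from hospital (if discharge happens earlier". It tests both by two-sided chi-square or Fisher exact test at 5%. SAP 8.2 and the protocol (synopsis, 3.1.3.1.1 and 7.1.1.2) use the same window, so it is not a slip in one place.

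SAP 10.6.2 also says "All secondary analysis will be done using ITT population", and for endpoint 1: "Time to discharge will be compared between the treatment groups using the Cox proportional hazard model".

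Death appears elsewhere too:
- Condition c of the primary endpoint (SAP 10.6.1): "The patient has survived and has not been re-admitted to hospital for COVID-19 management through Day 28".
- The worst-rank sensitivity analysis (SAP 10.6.1): "The highest (worst) ranks will be given to patients who die".
- Stage II item 2 (SAP 10.6.2) lists dying "until day 60 (regardless of whether patients are discharged from hospital before Day 28 or not", but its analysis sentence reads "Proportion of patients with disease worsening will be summarized by number and percentage".
- Tables of adverse events leading to death (SAP 10.7.1).
- Mortality comparisons at the interim, labelled exploratory and based on observed data (SAP Appendix I).

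Endpoint 14 measures days on each support as stop date minus start date plus one and compares the means by ANOVA. It has no rule for patients who die on support.

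**The concern.** A mortality comparison needs the same follow-up in both arms. Here follow-up ends at discharge, which happens after randomization and may be affected by treatment. If favipiravir speeds discharge, its patients are observed for death for less time, and a test of crude percentages cannot tell fewer deaths from less observation.

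The plan also treats the same patient in two ways. Someone discharged early who dies on Day 20 fails the primary endpoint and gets a worst rank, yet is not a death in the mortality endpoint.

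The guidance in Protocol Appendix I is nonbinding. It gives all-cause mortality at a fixed time of at least 28 days as an example endpoint, asks that time points be set in days after randomization, and calls mortality analyses important whatever the primary endpoint.

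The primary endpoint and the sample size are not at stake. What is at stake is the main safety check on the primary result: whether the trial can say how many patients in each arm were dead at Day 28.

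**Working it through.** **1. Where a death on Day 20 is counted, for a patient discharged on Day 9**

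| Analysis | Counted? | Tested, stand-alone, all-cause, Day 28, final analysis? |
|---|---|---|
| Endpoint 15 (SAP 10.6.2) | No | It would be, but its window closed on Day 9 |
| Primary endpoint, condition c | Yes, as not resolved | No, composite |
| Worst-rank analysis | Yes, worst rank | No, composite |
| Adverse events leading to death (SAP 10.7.1) | Yes, if reported | No test and no Day 28 cut |
| Stage II item 2 | Listed, to Day 60 | No; Day 60, and the analysis sentence names worsening only |
| Interim mortality (Appendix I) | Possibly | No, interim and exploratory |

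SAP 9.5.1 imputes only the clinical status score among efficacy data, so nothing covers unknown vital status at Day 28.

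**2. The plan's own figures**

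The documents state no mortality rate, effect or power. The sample size for the primary endpoint reproduces: 4 × (1.960 + 0.842)² / (ln 1.25)² = 631 events, and 631/0.85 = 742, or 371 per arm. Changing endpoint 15 does not touch these numbers.

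**3. Illustration of the error (all rates assumed)**

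Inputs: 80% of controls discharged and 5% dead in hospital by Day 28; discharge hazard ratio 1.25 (borrowed from the primary endpoint's assumption); the same in-hospital death hazard in both arms; constant hazards; 390 per arm.

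- Control total hazard: −ln(1 − 0.85)/28 = 0.06775 per day. Discharge a = 0.06775 × 0.80/0.85 = 0.06377; death m = 0.06775 × 0.05/0.85 = 0.00399. Favipiravir: 1.25a and m.
- Mean time observed in hospital, (1 − exp(−28(a + m)))/(a + m): 12.55 days control, 10.80 days favipiravir.
- Endpoint 15 is m times that: 5.00% vs 4.30%, a difference of −0.695 points and a risk ratio of 0.861.
- Deaths after discharge: integral from 0 to 28 of a·exp(−(a + m)t)·(1 − exp(−h(28 − t))) dt, with 1.25a for favipiravir. The post-discharge hazard h is k·m in control and r·k·m in favipiravir. k is taken below 1 because patients leave when judged fit.

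With equal post-discharge hazards (r = 1):

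| k | Uncounted deaths, control + favipiravir | True Day 28 mortality, control vs favipiravir | Overstatement of benefit (points) |
|---|---|---|---|
| 0.10 | 2.25 + 2.54 | 5.58% vs 4.95% | 0.073 |
| 0.25 | 5.59 + 6.30 | 6.43% vs 5.92% | 0.180 |
| 0.50 | 11.07 + 12.46 | 7.84% vs 7.50% | 0.356 |

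At r = 1 the error runs from 0.04 to 1.29 points over control discharge of 70–85% and control in-hospital mortality of 3–15%. It is 0 at a discharge hazard ratio of 1.0, 0.03–0.15 at 1.1 and 0.13–0.64 at 1.5.

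With unequal post-discharge hazards, for k = 0.10, 0.25, 0.50:
- r = 0.5: endpoint 15 understates the benefit by 0.25, 0.62, 1.22 points.
- r = 1.5: it overstates the benefit by 0.40, 0.98, 1.90 points. The true risk ratio is 0.95, 1.04, 1.15, while endpoint 15 still shows 0.86.
- The direction changes at r of about 0.89 on the risk difference and about 0.76 on the risk ratio.

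**4. Endpoint 14 (secondary)**

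Assume the stop date is the death date (the SAP does not say), 14 days of ventilation in survivors and 7 in those who die. At 30% mortality the mean is 0.3 × 7 + 0.7 × 14 = 11.9 days; at 50% it is 0.5 × 7 + 0.5 × 14 = 10.5 days. Higher mortality looks like shorter support. Over all patients, with 10% ventilated, the means are 1.19 and 1.05, a difference of 0.14 days.

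**The case against.** Endpoint 15 can be read as a deliberate in-hospital mortality endpoint. It shares its window with endpoints 12 to 14, consistently across both documents, and the appended guidance is nonbinding. Post-discharge deaths are not lost to the trial: besides the routes above, death is a recorded reason for discontinuation (Protocol 3.1.6.1.1) shown by arm in the disposition table (SAP 10.1), and adverse event outcomes include fatal (Protocol 9.1.1.6). The Stage II wording may be shorthand for the whole item, death included.

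On size, the assumed k of 0.10 to 0.50 means that 10%, 22% or 36% of control Day 28 deaths follow discharge, which nothing in the documents supports. At k = 0.01 about 0.5 deaths are missed and the error is 0.007 points. Even 0.07 to 0.36 points is small beside a standard error of 100 × √(2 × 0.05 × 0.95/390) = 1.56 points. The r = 0.5 and r = 1.5 cases suppose that the drug changes death after discharge but not in hospital, which is a strained assumption for a 10-day course.

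Most of this stands as a limit on size and scope. The omission is from endpoint 15, not from the whole plan; the bias may be small; and endpoint 14 rests on an inference. It does not supply the missing analysis: none of these routes is a tested stand-alone Day 28 proportion. A Day 60 test of death, if intended, would answer a different question and would need to be stated.

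**Conclusion.** The concern holds. It follows from the wording alone and needs no assumed rate: endpoint 15 omits deaths between discharge and Day 28, its window depends on an outcome that treatment may change, and nothing else in the final analysis fills the gap.

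The size and direction of any bias are unknown. With equal post-discharge hazards the error favours the faster-discharging arm: 0.07 to 0.36 points at the base assumptions and 0.04 to 1.29 over the ranges tried. With unequal hazards it can go either way. It is zero if no discharged patient dies by Day 28. Endpoint 14 is a lesser, related gap. The change is worth making because it is cheap and concerns mortality, not because a large bias has been shown.

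**What to change.** **Endpoint 15.** In both documents, count all deaths (any cause and COVID-19-associated) from randomization through Day 28 regardless of discharge, in all ITT patients. Survival to Day 28 is already needed for condition c. Add an alive/dead entry to the existing Day 28 call, because vital status is not among the named telephone items (Protocol 6.3.1.6). State a rule for unknown status, since patients who discontinue or are lost to follow-up may have none. In-hospital death can stay as a supportive summary.

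**Stage II.** Analyse dying to Day 60 as its own item, separate from disease worsening.

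**Endpoint 14.** State what the stop date is for a patient who dies on support, and keep the durations as descriptive tables. As a supplementary analysis only, add days alive and free of each support to Day 28, with death scored 0. Note that support data are scheduled only to discharge, with optional collection at additional visits (Protocol Table 2, footnote 21), so later support could be missed.

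**Cost.** Revised wording in the SAP and protocol, one data field and one missing-status rule. There are no new visits and no change to the primary analysis or sample size.
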